9.3 Vital Signs

Summary statistics (n, mean, SD, minimum, median, and maximum) will be presented for the observed values for sitting systolic and diastolic blood pressure, pulse, respiration rate, and oral temperature at baseline and each post dose time point by treatment group for the safety population. Summary statistics will also be presented for the change-from-baseline values to each post baseline time point. In these displays, baseline will be defined as the last non-missing value obtained prior to first dose of study medication for Period 1, Day 1 predose.

All vital signs results will be displayed in subject listings.

9.4 Electrocardiograms

Single ECG results will be collected at Baseline/Screening and at Week 6 and Week 12 of each study period. For the quantitative variables of QRS interval, PR interval, QT interval, QTcB interval, and Heart Rate, summary statistics (n, mean, SD, minimum, median, and maximum) will be presented for the observed values at Baseline/Screening and each post dose time point. Summary statistics will also be presented for change-from-baseline values to each post baseline time point. In these displays, baseline will be defined as the last non-missing value obtained prior to first dose of study medication for Period 1, Day 1 predose.

All ECG results will be displayed in subject listings.

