In dog toxicology studies of 28-days and 13-weeks, the no observed adverse effect level (NOAEL) for BPN14770 was 30 mg/kg. At 100 mg/kg in the 28-day study, BPN14770 caused inappetance and weight loss and in female dogs an approximately 30 msec increase in QTc with a concomitant increase in heart rate of 10 bpm. There were no changes in hematology or ophthalmology. Macroscopic observations included pale livers in two of eight animals at 100

mg/kg which correlated with mild alanine transaminase (ALT) elevation only in those two animals. Microscopic changes of periportal hepatocellular cytoplasmic vacuolation were observed in the livers of one male and two female dogs at 100 mg/kg. No liver changes were observed in recovery dogs suggesting that these changes, if present, were reversible.

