8.8 Electrocardiograms

Single 12-lead ECGs will be performed at every clinic visit except the Week 1 visit during each Period as specified in the Schedule of Assessments.

ECGs should be obtained after the subject has been resting comfortably in a supine position for approximately 5 minutes. ECGs will be collected prior to blood collection whenever possible.

ECGs will be assessed locally for eligibility determinations and safety. All ECG traces will be kept as source data.

For purposes of qualifying any given subject for study participation based on Inclusion/Exclusion Criteria, clinically significant out-of-range results may be repeated once.

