11.5 Safety Analysis

Safety analysis will be based on all subjects receiving at least one dose of study medication. Treatment emergent AEs will be summarized based on the frequency of AEs and their severity for all dosed subjects. Adverse Events (AEs), including clinically meaningful laboratory abnormalities and significant behavioral changes, will collected. AE severity and relatedness to treatment will be assessed. AEs will be tabulated for placebo and BPN14770 treatments using preferred terms and system organ classes. Summaries will also be provided by severity and relationship to treatment. Serious Adverse Events (SAEs) will be summarized separately, in a manner similar to that used for Adverse Events.

Overall safety and tolerability will be assessed by clinical and/or statistical review of all safety parameters including adverse experiences, laboratory values, vital signs, physical exams, and ECG data. General clinical and laboratory adverse events will be presented in frequency tables. Summary statistics (n, mean, SD, median, and range (minimum, maximum) will be tabulated for the observed values and the change (or percent change) from baseline for all continuous parameters for vital signs, ECG, and laboratory tests.

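### SAP 9.4 tabulates Bazett as its only rate-corrected QT, so a heart-rate difference between BPN14770 and placebo could appear as, or mask, a QTc change; a Fridericia row would cost almost nothing

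*SAP*

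**What the plan says.** SAP 9.4 Electrocardiograms sets out summary statistics "For the quantitative variables of QRS interval, PR interval, QT interval, QTcB interval, and Heart Rate", as observed values and as change from the pre-dose Period 1 baseline: "Summary statistics will also be presented for change-from-baseline values to each post baseline time point". It adds that "All ECG results will be displayed in subject listings". SAP 4.2 supplies the general rule that results are shown by treatment group or sequence where appropriate.

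The protocol names no correction formula. Its safety analysis (11.5) asks only for descriptive statistics of observed values and "change (or percent change) from baseline for all continuous parameters for vital signs, ECG, and laboratory tests". Neither document sets a QTc threshold, test or decision rule for the analysis.

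Protocol 4.3.1 has two statements on dogs:
- At 100 mg/kg in the 28-day toxicology study there was, "in female dogs an approximately 30 msec increase in QTc with a concomitant increase in heart rate of 10 bpm". The no-observed-adverse-effect level was 30 mg/kg.
- Earlier in the same section, cardiovascular function in dogs is said to be unaffected at doses up to 100 mg/kg.

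In humans, Protocol 4.2 reports no ECG or vital-sign changes in the single-dose study. Protocol 4.3.2.2 reports no clinically significant ECG or vital-sign effects in the 8-day multiple-dose study.

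**The concern.** Bazett divides QT by the square root of RR. If QT in fact varies less steeply with RR, the correction overshoots: QTcB rises when heart rate rises and falls when it falls, with repolarisation unchanged. The only QTc finding described in the protocol came with a faster heart rate, which is the combination in which this matters.

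What is at stake is how a named safety endpoint is read. If BPN14770 changed heart rate relative to placebo, the one planned QTc row would mix that change with any true QTc effect. A second correction chosen only after QTcB had been seen would be open to the charge of being picked for its answer. Naming it in the SAP avoids that.

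**Working it through.** **No plan figure to reproduce.** The documents give no expected QTc, heart rate or QTc-based sample size, so the size of the artefact is computed directly.

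**Assumptions, none from the documents.** QTc 400 ms when standardised to 60 bpm; starting heart rate 55–90 bpm; true QT–RR exponent b between 0.25 and 0.40, with 1/3 (Fridericia) as base case. The 10 bpm step matches the size of the dog heart-rate change and is used only as an example.

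**Formulas.** RR = 60/HR (seconds). With no repolarisation change, QT = 400 × RR^b. Then:
- QTcB = QT / RR^(1/2) = 400 × (HR/60)^(1/2 − b)
- QTcF = QT / RR^(1/3) = 400 × (HR/60)^(1/3 − b)

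QTcB is free of heart rate only if b = 0.5.

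**Base case, b = 1/3.** QTcB = 400 × (HR/60)^(1/6), which is 400.0, 410.4, 419.6 and 428.0 ms at 60, 70, 80 and 90 bpm. QTcF stays at 400 by construction.

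**QTcB shift for a 10 bpm rise with no true effect (ms):**

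| Starting HR (bpm) | b = 0.25 | b = 1/3 | b = 0.40 |
|---|---|---|---|
| 55 | +16.7 | +11.1 | +6.7 |
| 60 | +15.7 | +10.4 | +6.2 |
| 70 | +14.1 | +9.2 | +5.5 |
| 80 | +12.8 | +8.3 | +4.9 |
| 90 | +11.8 | +7.6 | +4.4 |

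The full range is about +4 to +17 ms. At b = 1/3, a 5 bpm rise gives +3.9 to +5.8 ms, and a 10 bpm fall gives −8.3 to −13.0 ms.

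**Masking, b = 1/3.** Add a true 10 ms QTc increase and let heart rate fall by 10 bpm from 65–80 bpm. QTcB then changes by only −1.3 to +1.0 ms. With a 10 bpm rise instead, it changes by +19.0 to +20.2 ms.

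**QTcF is not exact either.** From 60 to 70 bpm:
- b = 0.25: QTcF moves by 400 × (70/60)^(1/12) − 400 = +5.2 ms, against +15.7 for QTcB.
- b = 0.40: QTcF moves by 400 × (70/60)^(−1/15) − 400 = −4.1 ms, against +6.2 for QTcB.

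QTcF is the less rate-dependent of the two while b is nearer 1/3 than 1/2, that is, below about 0.42. This is a reason to show both.

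**What the QT and heart-rate rows can tell a reader.** In the 60-to-70 bpm base case, QT falls from 400 to 380.0 ms, so the table would show heart rate +10, QT −20 and QTcB +10. With a true 10 ms effect, QT would go from 400 to 410 × (60/70)^(1/3) = 389.5, a fall of about 10 ms. Group means could therefore point to a rate effect. But QTcF is a nonlinear function of each tracing's QT and heart rate. Its mean can only be approximated from the two mean rows. Its SD depends on how QT and heart rate vary together, and its minimum and maximum need not come from the tracings with extreme QT or heart rate. The listings contain what is needed; the planned tables do not.

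**The case against.** The strongest reply is that the planned table already holds uncorrected QT and heart rate, all ECG results are listed, and so nothing is lost. A reader might infer from the single QTc row that the output could not separate a rate effect from a repolarisation effect. The documents do not support that: group means of QT and heart rate would often reveal the pattern, and QTcF can be derived later from data already collected. What remains is a gap in planned output, not in data capture.

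A shift in heart rate common to both treatments cancels in the drug–placebo comparison. This stands: the problem needs a heart-rate difference between treatments.

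A reader might also take the dog result as evidence that BPN14770 prolongs QTc or speeds the heart in patients. It is not. It was seen in females, above the no-effect dose, while this trial enrols only men. The same section reports no cardiovascular effect in dogs up to that dose, and the human studies cited describe no ECG signal. The multiple-dose study covered 10–50 mg twice daily, which brackets the 25 mg twice daily used here, although for 8 days rather than 12 weeks. The correction used in dogs is not stated, so the modelled shifts should not be expressed as a fraction of the 30 ms finding.

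Finally, no planned decision turns on QTcB. ECGs are single tracings read locally, clinical significance is the investigator's judgement, and the analysis is descriptive. That limits the weight of the point. It does not make the extra row less useful.

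**Conclusion.** The point holds as a precaution and is a free improvement. QTcB is the only rate-corrected QT planned, and under the stated assumptions a 10 bpm heart-rate difference between treatments would move it by about 4 to 17 ms in the same direction with no repolarisation change (about 8 to 10 ms from 60–80 bpm at exponent 1/3). A fall in heart rate of that size could hide a true increase of about 10 ms. These sizes rest on an assumed QTc, heart rate and exponent. Nothing in the documents shows that BPN14770 changes heart rate in humans. The plan is not defective without the change, but its ECG table would be easier to interpret with it.

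**What to change.** In SAP 9.4, add QTcF to the listed variables, derived for each tracing as QT / (60/HR)^(1/3) from the recorded QT and heart rate. Include it in the observed-value and change-from-baseline summaries, state that these are by treatment group, and keep QTcB beside it. The cost is one derived variable and extra rows in an existing table, with no new data collection.

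Two related passages need reconciling. Protocol 4.3.1 should square its statement of no cardiovascular effect in dogs up to 100 mg/kg with the QTc and heart-rate finding at that dose. Separately, the ECG visits differ: the SAP states "Single ECG results will be collected at Baseline/Screening and at Week 6 and Week 12 of each study period", Protocol 8.8 states "Single 12-lead ECGs will be performed at every clinic visit except the Week 1 visit during each Period", and the protocol's Schedule of Assessments and visit lists show ECGs at Weeks 2 and 12 but not at Week 6. The table shell, including the new rows, should follow whichever visits are confirmed.

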10 SUBJECT LISTINGS

Data that are collected and entered into the study database but that are not displayed in the summary tables specified in the preceding sections will be presented in subject listings. These will include (but will not be limited to) data from the following data collection modules:

Protocol Deviations

Drug Accountability/Dosing Information

Inclusion/Exclusion Criteria

Tetra Discovery Partners Inc.

Statistical Analysis Plan Tetra Discovery Partners BPN14770-CNS-203

Caregiver Information Concomitant Medications Concomitant Treatments/Procedures Stanford-Binet Non-Verbal and Verbal Intelligence Scale Substance Abuse Suicidality Assessment

11 INTERIM ANALYSES

No statistical interim analyses are planned.

Version 1.0 16 July 2020

14 REVISIONS TO STATISTICAL ANALYSIS PLAN

Date	Revision	Statistician's Signature
•	•	•
•	•	•
•	•	•
•	•	•
•	•	•
•	•	•

15 APPENDIX

Version 1.0 16 July 2020

15.1 Conventions for Statistical Tables and Subject Listings

The following conventions are used in the mockups for the statistical tables and subject listings:

[Sponsor] = [Tetra Discovery Partners]

[Protocol] = [BPN14770-CNS-203]

[Drug name] = [BPN14770]

Subject number in listings will represent the subject's screening number.

In general, font size will be at least 9-point and all margins will be 1 inch.
